- Immunosuppressant medications
 - Current or recent (<3 months) treatment with anti-neoplastic agents
 - Current or recent (<3 months) treatment with calcineurin inhibitors (tacrolimus, cyclosporine)
 - Current or recent (<3 months) treatment with mycophenolate mofetil
 - Current or recent (<3 months) treatment with monoclonal antibodies to B and T-Cells, anti-TNF, glucocorticoids, antimetabolities (azathioprine, 6-mercaptopurine)
- Neutropenia with absolute neutrophil count (ANC) <0.5 x 10⁹/L
- Active gastroenteritis due to infectious cause other than CDI
- Short gut syndrome
- Colostomy
- Ascites
- End-stage liver disease
- Untreated, in-situ colorectal cancer
- Irritable bowel syndrome
- Inflammatory bowel disease including Crohn's disease and ulcerative colitis
- Microscopic colitis including collagenous colitis and lymphocytic colitis
- Severe food allergy (anaphylaxis) that cannot be confirmed as having been excluded from a donor's diet within the five days prior to donation
- Anorectal disorder/severe rectal sphincter tone abnormality or inability to retain enema material
- Unable or unwilling to tolerate colonoscopy/sigmoidoscopy, colonoscopy prep, or enema for any reason at discretion of MD
- Severe underlying disease that the patient is not expected to survive for the subsequent 12 months at the discretion of the MD.
- Any conditions for which, in opinion of MD, the treatment may pose a health risk

Target enrollment and rationale

The longitudinal cohort sample size (n=150) was chosen to allow recruitment in a suitable time frame. Strong consideration will be given to resubmitting documentation including IND amendment and IRB ammendment for a larger sample size and/or prolonged follow-up at the completion of the study.

III. Design Methodology

IV. Therapeutic Administration: Fecal Microbiota Transplantation Protocol

Donor selection, laboratory screening, and monitoring

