- Any new medical conditions / new medications with associated clinical course
- Any changes in pre-existing medical conditions with associated clinical course

5. Long-term assessment II (Month 12 – Telephone Assessment)

- Study patient identifier
- Date
- Self-reported height and weight, resulting calculated BMI
- Any recurrence of CDI with description of clinical course, including additional treatments received
- Assessment of any new SAEs
- Any new medical conditions / new medications with associated clinical course
- Any changes in pre-existing medical conditions with associated clinical course

Data Analysis

Primary Study: Safety and Efficacy (Aims 1-3)

Safety endpoints will be collected with raw events and crude rates reported for overall cohort. Clinical cure rates will be calculated at each site. Both unweighted pooled clinical cure rates and weighted pooled clinical cure rates will be calculated with corresponding 95% confidence interval (CI) for overall study, as well as pre-defined

subgroups including: age, gender, modified Horn index, delivery modality, donor, retention time, site. Weighted pooled rates will be analyzed using the random effects model (DerSimonian-Laird method). Heterogeneity across sites will be assessed using the I² statistics and the Cochran Q test, where I² > 50% or Cochrane Q < 0.10 will be considered to indicate significant heterogeneity. Statistics will be performed using Stata SE 12.0 (StataCorp, College Station, TX).

Secondary Study: Microbiome (Aim 4)

DNA will be extracted from each frozen specimen collected from both donors and recipients. The V4 region of the 16S rRNA gene will be amplified using multiplexed bar-coded primers as previously described.²⁷ Up to 192 samples will be pooled onto a single lane of an Ilumina MiSeq for high-throughput sequencing. Quality trimmed and filtered sequence data will be clustered into Operational Taxonomic Units (OTUs) for computational analysis. Each recipient will receive an engraftment score based on their similarity (as quantified by the Jensen-Shannon Divergence) to the donor used in their FMT. Recipients will also be assessed for the long-term stability of their community and it's similarity to samples collected and previously published from both healthy and dysbiotic patients.

VI. Adverse Event Monitoring

We will capture both short and long-term safety profiles, including:

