For individual subjects enrolled in the study: any subject who has an SAE related to FMT will be ineligible for a second FMT during the course of the study.

FDA/CBER will be notified by phone or fax within 48 hours if the study is halted for review.

VII. Minimizing Risks to Human Subjects

VII-A. Human Subjects Involvement, Characteristics and Design

1. IRB approval for stool donor program has been obtained; Local site IRB approval from *each* study center will be obtained subsequent to required FDA approval of IND.

2. Subjects will be given informed consent using the standard consent process for colonoscopy/enema. Additional theoretical risk for transmission of infectious agents, and other diseases and conditions will also be discussed.

3. Donors will be given informed consent and will tested for most common infectious agents. Individuals with communicable disorders or a history of high-risk behaviors will not be permitted to donate.

4. Protections against risk are provided in detail below.

A sample size of 150 patients will be recruited. These patients will have been treated at or referred to one of the study centers for management of recurrent CDI.

Additional sites may be asked to join this study as needed to expeditiously achieve the targeted enrollment. The initial study sites will include:

1. Brown University and Women's Medicine Collaborative Providence, Rhode Island

2. Indiana University Health University Hospital Indianapolis, Indiana

3. University of Virginia Health Systems Charlottesville, Virginia

4. Edward Hospital Naperville, Illinois

This will be an open-label, longitudinal cohort study with follow-up at Day 3, Week 6, Month 6 and Month 12. The estimated duration of this study is 24 months. No patient will be excluded from recruitment on the basis of ethnicity, race, or disability. Subjects are expected to range in age from 18-75. Subjects will all be outpatients and will likely have comorbidities. All subjects will be fully informed about the purposes of the study, and risks and benefits of the study, and informed consent for all phases of the study will be obtained. Patients who agree to participate will be free to withdraw from the project at any time.

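### The site-heterogeneity rule compares Cochran's Q itself, not its p-value, with 0.10; the limb is inverted as printed, with very small effect at the four listed sites (minor)

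*Combined protocol and SAP*

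**What the plan says.** In the combined protocol and SAP, Section 6, part V, Data Analysis, Primary Study (Aims 1-3), cure rates are calculated at each site and then pooled, both unweighted and weighted. The weighted rate uses the DerSimonian-Laird random effects model. On consistency between sites the plan says: "Heterogeneity across sites will be assessed using the I² statistics and the Cochran Q test". The criterion follows in the same sentence: I² above 50%, or the limb at issue here, "Cochrane Q < 0.10 will be considered to indicate significant heterogeneity". The words p-value and significance level do not appear in this rule, and no other section supplies them.

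Part VII-A lists four centres under "The initial study sites will include" and adds: "Additional sites may be asked to join this study as needed to expeditiously achieve the targeted enrollment". No upper limit on the number of sites is given. The target is 150 subjects, chosen for feasibility (part II, Target enrollment and rationale).

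**The concern.** Q is a weighted sum of squared deviations of the site rates from their pooled value. It is 0 when all sites have the same rate and increases with disagreement; large Q, and hence a small p-value, is evidence of heterogeneity. A rule that calls Q < 0.10 significant heterogeneity therefore flags agreement. It also conflicts with the limb beside it: I² > 50% requires a large Q, while the other limb requires Q close to 0.

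Two things could follow if the sentence were programmed as printed. Sites with virtually equal cure rates could be reported as heterogeneous. And the Q test that was meant would be absent, leaving I² > 50% to do all the work. What is at stake is the statement the study makes about whether its centres gave consistent cure rates.

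**Working it through.** **Inputs from the document.** Rule: I² > 50% or Q < 0.10 (Data Analysis). Sites: k = 4 initially, more allowed (VII-A). N = 150 (VII-A). Expected cure rate 80–90% (Specific Aims, SA3). The plan gives no calculated figure for this rule, so there is nothing to reproduce first.

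**Assumptions.** Equal site sizes, cure rate 85%, between-site logit SD 0.4 to 0.8, and up to 10 sites. None of these is stated in the plan.

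**Formulas.** With site rates yᵢ and inverse-variance weights wᵢ, Q = Σ wᵢ(yᵢ − ȳ)², where ȳ is the weighted mean. Under homogeneity Q is referred to chi-square with k − 1 df, upper tail. I² = max(0, (Q − df)/Q), so I² > 50% is the same as Q > 2·df.

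**Direction of the printed limb, four sites (df = 3).**
- Q = 0.10 has an upper-tail p of 0.992 and I² = 0%.
- Four sites with 32/37 cured each: Q = 0, p = 1, I² = 0%. The printed rule flags them.
- Sites with 32/37, 33/38, 32/38 and 32/37 cured: Q = 0.13 on the raw scale. They are not flagged. The false flag needs almost exact agreement.

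**Thresholds and chi-square probabilities of a flag when sites are identical.** Printed = P(Q < 0.10) + P(Q > 2·df). Intended = P(Q exceeds the smaller of the two critical values).

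| Sites | P(Q < 0.10) | Q for p < 0.10 | Q for I² > 50% | p at I² = 50% | Printed | Intended |
|---|---|---|---|---|---|---|
| 4 | 0.8% | 6.251 | 6 | 0.112 | 12.0% | 11.2% |
| 5 | 0.12% | 7.779 | 8 | 0.092 | 9.3% | 10.0% |
| 6 | 0.02% | 9.236 | 10 | 0.075 | 7.5% | 10.0% |
| 10 | <0.01% | 14.684 | 18 | 0.035 | 3.5% | 10.0% |

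At four sites the I² threshold (6) lies below the Q-test threshold (6.251), so anything with p < 0.10 is already flagged by I². From five sites the order reverses, and the p-value limb would add detections that the printed rule misses.

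**Simulation at four sites** (logit scale, 0.5 correction for sites at 0% or 100%).
- Identical sites: 7.4% flagged as printed, 7.0% as intended. The difference, about 0.4%, is the false flag from Q < 0.10.
- Logit SD 0.8: 59.6% as printed, 59.5% as intended.

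**Simulation at more sites**, ranges over logit SD 0.4 to 0.8.
- 6 sites: 12–49% printed, 16–54% intended.
- 10 sites: 2–22% printed, 6–39% intended.

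**A second assumed pattern**, half the sites at 95% cure and half at 75%: 88.0% under both rules at 4 sites; 60.5% printed against 68.7% intended at 6; 10.4% against 31.0% at 10.

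The simulated rates move by a few percentage points with the rounding of site sizes and the handling of the 0.5 correction. The ordering does not change.

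**The case against.** The strongest reply is that this is a drafting slip with only one sensible reading. The plan names the Cochran Q test and then gives a less-than-0.10 cut-off, which is how a p-value is compared. The literal reading contradicts the other half of its own sentence, so a competent analyst would be unlikely to apply it. That largely stands, and it is why the point is minor. It does not remove the point: a pre-specified criterion should not depend on a reader reversing it.

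The reply is also right that no analysis hangs on the flag. Random-effects pooling is used whatever it says, and the site rates and both pooled rates are reported regardless.

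A reader might infer more than the documents support, in four ways.
- *That false flags would be common.* At two sites, P(Q < 0.10) under homogeneity is 24.8%. But the rule is stated for heterogeneity across sites, the plan lists four, and it does not describe a two-site analysis or say that the test is run within subgroups.
- *That the rule decides whether a pooled cure rate may be reported.* The plan attaches no such decision to it.
- *That joining the two limbs with 'or' is an error because it fixes no error rate.* The plan claims no error control for this screen; keeping or dropping the 'or' is a matter of preference.
- *That a corrected p < 0.10 test alone would hold a 10% false-positive rate at any number of sites.* In simulation with identical sites it fires in about 6% of trials at four sites and 1% at ten, because Q on small site samples does not follow chi-square closely.

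**Conclusion.** The limb is wrong as written: it compares the statistic instead of its p-value with 0.10, and so runs in the wrong direction. The direction error needs no assumption; its size depends on the number of sites. At the four listed sites the printed and intended rules give almost the same result. The loss of the intended test begins at five sites and becomes visible at six to ten. How many sites will join, how subjects divide among them and how much cure rates vary between them are not in the plan, so the 6- and 10-site figures illustrate a range and do not predict this study.

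The consequence is confined to the reported conclusion on site consistency. Pooled cure rates, their confidence intervals and the safety results are untouched. Severity: minor.

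**What to change.** In the Data Analysis section, insert the words *test p-value* between Q and the 0.10 cut-off and correct the spelling to Cochran, so that the criterion reads: *I² > 50% or Cochran Q test p-value < 0.10*. Keep the rest of the sentence, including the 'or', and add no claim about a fixed false-positive rate. The cost is a few words in one sentence, with no new data, no added procedures for subjects and no change to any other analysis.

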The design will be a prospective, open-label, multi-center longitudinal cohort study to assess the short- and long-term safety of FMT as well as the clinical resolution of diarrhea among 150 patients with 3 or more episodes of CDI (defined as 3 unformed stools over 24 hours for 2 consecutive days and either a positive stool test for CDI or pseudomembranes on colonscopy/sigmoidoscopy).²⁶ Subjects will be adult outpatients referred to one of the study centers after at least three recurrent episodes of CDI and previous treatment with at least one 10-day course of oral vancomycin or fidaxomicin. After FMT by colonoscopy/sigmoidoscopy or enema, patients will be followed prospectively and monitored for clinical resolution and adverse events at: 3 days (telephone), 6 weeks (clinical assessment), 6 months (telephone or clinical assessment), and 12 months (telephone or clinical assessment) after FMT. Subjects who recur will be offered a second FMT by colonoscopy with a different donor. Microbiome analysis will be conducted from stool samples at baseline and each of the 4 follow-up intervals.

III. Product Name/Chemical Structure

Fecal Microbiota Preparations

IV. Proposed Indication(s)

Recurrent Clostridium difficile infection

V. Dosage, Route of Administration and Dosing Regimen

V-A Colonoscopic/sigmoidoscopic FMT (FMP250)

Dosage Form: Screened human donor stool,

homogenized, filtered and aliguoted to sterile 250mL

vessels.

Route of Administration: Infusion will occur in the most proximal region of the colon that is technically feasible. The material will be infused through the working channel of the endoscope.

Dosing Regimen: 250 mL x 1 dose. In the event of a clinical non-response (defined in 'Protocol' Section), a repeat single 250 mL dose will occur from a different donor.

V-B Retention Enema FMT (FMP250E)

Dosage Form: Screened human donor stool,

homogenized, filtered

and aliguoted to sterile 250mL

vessels.

Route of Administration: Lubricated enema nozzle will be inserted into rectum and contents expelled into the distal colon with the subject requested to retain material for at minimum 30 minutes.

Dosing Regimen: 250mL x 1 dose. In the event of clinical non-response (defined in 'Protocol' Section), a repeat single 250 mL dose via colonoscopy will occur from a different donor.

4. [RESERVED, CFR 312.23]

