SA4. Collect pre- and post-FMT stool samples from patients with recurrent CDI as well as donor stools for microbiome analysis.

Hypothesis: Prior to FMT, recurrent CDI patients will have deficiencies of certain normal colonic flora.²² After FMT, these microbial populations will be restored, resulting in a durable transition to a diverse, stable community that resembles the composition of the healthy stool donor. We expect that this transformation will be stable in the absence of challenge with antimicrobial therapy.

II. Subject Inclusion/Exclusion Criteria

Definitions

- **Clostridium difficile infection**: At least 3 unformed stools over 24 hours for 2 consecutive days and either positive stool test (ELISA or PCR) for *Clostridium difficile* toxins or pseudomembranes on colonoscopy (SHEA-IDSA guidelines).²⁶
- **Clinical Cure**: Clinical resolution of diarrhea (<3 unformed stools for 2 consecutive days) with maintenance of resolution at 6-week follow-up period, at minimum, and no further need for antibiotic therapy for CDI. In keeping with SHEA-IDSA guidelines and an absence of 'test of cure,' subjects who meet aforementioned definition will be considered a clinical cure regardless of any incidental follow-up stool testing employed.²⁶
- **Clinical Non-Response:** Ongoing or development of diarrhea and the requirement for antibiotic therapy for CDI.

Inclusion criteria

- Adult (age 18-75 years old)
- Outpatient
- Third or further documented CDI episode and
- Unable to maintain CDI cure after standard therapy with oral vancomycin or fidaxomicin
 - Previous treatment with at least one course of tapered/pulse vancomycin or
 - Inability to taper or stop vancomycin or fidaxomicin without developing diarrhea requiring antibiotic therapy.
- Improvement of CDI symptoms on vancomycin or fidaxomicin

Exclusion criteria

[figure not shown]
- Unable to comply with study follow-up procedures at discretion of MD
- Unable to provide informed consent at discretion of MD
- Participating in another clinical trial
- Pregnant or nursing currently or planned pregnancy in next 1 year
- Evidence of toxic megacolon or gastrointestinal perforation
- Peripheral white blood cell count >30 x 10⁹/L and/or temperature >38 degrees Celsius
- Admission to an intensive care unit within prior 7 days for any reason
- Previously undergone FMT
- Severely immunocompromised patients

- HIV infection (any CD4 count)
- AIDS-defining diagnoses
- Inherited/primary immune disorder

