2. Baseline status, at MD discretion, will be conducted: HIV (type 1 and 2), hepatitis A (IgM, G), hepatitis B (HBsAg, anti-HBcIgM and anti-HBcIgG), hepatitis C (HCV antibody), and Treponema pallidum screening (EIA with reflex to RPR).

3. Baseline complete blood count, liver function panel, creatinine and random blood glucose, and stool *C. difficile* PCR will be documented prior to FMT.

B. Pre-Treatment Medications

1. Subjects will complete at least a 10 day course of vancomycin or fidaxomicin for the most recently diagnosed acute CDI prior to undergoing FMT.

2. To minimize symptoms, antibiotic therapy will be continued by subjects until 3 days prior to the FMT procedure then subsequently discontinued.

3. Any probiotics will be continued by subject until 3 days prior to the FMT procedure then subsequently discontinued.

4. The day before the procedure, the subject will be prepped with standard bowel prep if undergoing colonoscopic/sigmoidoscopy delivery at MD discretion. Patients receiving FMT via enema administration need not undergo a bowel prep at MD discretion.

C. Specimen Collection

Patients must be willing and able to provide stool samples for microbial characterization via high-throughput 16S rRNA sequencing. Patients will be asked to provide a baseline stool sample prior to the FMT procedure (Day 0), as well as follow-up stool samples collected at Day 3, Week 6, Month 6 and Month 12 after FMT.

Samples will be collected with a standard stool collection hat. Immediately after passage, approximately 1 gram of stool will be suspended in 5 ml of RNALater (Life Technologies) using a para-pak collection vial with embedded scoop (Meridian Biosciences). Samples will then be shipped at room temperature to the OpenBiome study site where they will be frozen within 7 days of passage, consistent with the technical specifications for stabilization of nucleic acids in RNAlater. To avoid contamination of the OpenBiome production facility, sample processing and sequencing will take place at the Massachusetts Institute of Technology in a BL-2 laboratory with appropriate containment.

D. Female Subjects:

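### The engraftment score has no baseline term and no other-donor comparison, so prior resemblance and general recovery both count as engraftment of the donor used

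*Combined protocol and SAP*

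**What the plan says.** The score is defined in one sentence of section 6, V, Data Analysis, Secondary Study: Microbiome (Aim 4): "Each recipient will receive an engraftment score based on their similarity", measured by Jensen-Shannon Divergence, to the donor whose stool they received. No formula, time point or reference value follows. The next sentence plans a separate look at long-term stability and at similarity to previously published healthy and dysbiotic samples.

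The SA4 hypothesis in section 6, I concerns a change. Recipients are expected to lack certain flora beforehand, and then "After FMT, these microbial populations will be restored", ending in a community that resembles the donor's.

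The material for a baseline reference is already in the plan. Section 6, IV, Specimen Collection asks for a Day 0 stool before the procedure and "follow-up stool samples collected at Day 3, Week 6, Month 6 and Month 12 after FMT". The General Investigational Plan (section 3, II) adds: "Microbiome analysis will be conducted from stool samples at baseline and each of the 4 follow-up intervals". For sequencing, "DNA will be extracted from each frozen specimen collected from both donors and recipients".

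A subject can have two donors. Section 3, II says: "Subjects who recur will be offered a second FMT by colonoscopy with a different donor". Section 6, IV (In the event of clinical non-response) likewise allows a second procedure with an alternate donor, after a 10-day antibiotic course, with follow-up continuing per protocol.

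**The concern.** Similarity to the donor is a level, whereas engraftment as SA4 frames it is a movement. A level cannot separate three cases: a recipient who took up the donor's community, one who already resembled it, and one who recovered towards a healthy community in general. Donors are healthy by selection, so recovery of any kind should raise similarity to all of them.

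If Day 0 similarity varies between recipients, that variation enters the score as noise. If it is also related to outcome, any comparison of the score between cured and non-responding subjects mixes starting point with treatment effect.

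The donor reference is also ambiguous for re-treated subjects. All of them are first-FMT non-responders, so the ambiguity falls unevenly across outcome groups.

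**Working it through.** The documents give no numerical value, SD or power figure for the score, so there is no stated result to reproduce. What follows illustrates the mechanism under assumed values.

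**Model (assumed).** The donor community and a non-donor community share no taxa. A recipient with donor-like share s is the mixture (s, 1−s), and the donor is (1, 0). With base-2 logarithms, H(s) the entropy of (s, 1−s), and midpoint ((1+s)/2, (1−s)/2):

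JSD(s) = H((1+s)/2) − ½·H(s), and similarity = 1 − JSD.

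**One case by hand.** Take s = 0.2 at Day 0 and no change after FMT. The midpoint is (0.6, 0.4), with entropy 0.971, and H(0.2) = 0.722. So JSD = 0.971 − 0.361 = 0.610 and similarity = 0.39. True engraftment is zero, but the score is 0.39.

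**Step 1: no change after FMT.** For baseline shares of 0 / 0.1 / 0.2 / 0.3 / 0.5 the unadjusted score is 0.00 / 0.24 / 0.39 / 0.51 / 0.69. Any baseline-referenced score is 0 throughout.

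**Step 2: post-FMT share 0.7, varying baseline.** Let e be the fraction of the non-donor part that is replaced, so post share = b + (1−b)e and e = (0.7−b)/(1−b).

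| Baseline share b | 0 | 0.1 | 0.2 | 0.3 | 0.5 |
|---|---|---|---|---|---|
| True e | 0.70 | 0.67 | 0.63 | 0.57 | 0.40 |
| Unadjusted similarity | 0.83 | 0.83 | 0.83 | 0.83 | 0.83 |
| Raw difference, JSD(Day 0) − JSD(post) | 0.83 | 0.59 | 0.44 | 0.32 | 0.14 |
| Proportional reduction, difference / JSD(Day 0) | 0.83 | 0.78 | 0.72 | 0.66 | 0.46 |

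The unadjusted score does not move as e falls. The raw difference over-corrects because it cannot exceed the Day 0 JSD: at b = 0.5 its ceiling is 0.31.

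**Step 3: correlation with e across recipients.** Here e is uniform on 0 to 1, b is independent of e and uniform from 0 to the stated maximum, and JSD has no measurement error (400,000 simulated recipients per column).

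| Baseline share up to | 0.05 | 0.1 | 0.2 | 0.3 | 0.5 | 0.7 |
|---|---|---|---|---|---|---|
| Unadjusted | 0.98 | 0.98 | 0.97 | 0.95 | 0.89 | 0.80 |
| Raw difference | 0.97 | 0.96 | 0.92 | 0.88 | 0.77 | 0.66 |
| Day 0 JSD as covariate | 0.98 | 0.98 | 0.98 | 0.97 | 0.95 | 0.91 |
| Proportional reduction | 0.98 | 0.98 | 0.99 | 0.99 | 0.99 | 0.99 |

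The covariate form never does worse than the unadjusted score, and it helps as baselines spread. The raw difference is worse than no adjustment in every column. The proportional form is flattered by a model in which engraftment is itself a proportional replacement. With noisy data it would be unstable where Day 0 JSD is small.

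**Step 4: what baseline adjustment cannot settle.** Recovery towards a general healthy profile lowers JSD to every donor, including those not received. Adjusting for Day 0 leaves that in the score. Only the contrast with donors not received isolates the donor-specific part.

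**Step 5: second FMT.** Stool is scheduled at Day 0, Day 3, Week 6, Month 6 and Month 12, counted from FMT, and none is tied to a second procedure. If re-treatment comes before the Week 6 sample, the last earlier stool is Day 3, taken before the 10-day antibiotic course if diarrhoea returned later.

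**The case against.** The strongest reply is that the plan is brief here rather than wrong. A reader might infer that it has decided to use post-FMT similarity alone and discard the baseline. The text does not say so: it names no sample, says only that the score is based on similarity, and elsewhere commits to analysing the Day 0 stool. This stands. The defect is a definition with no baseline term, not a stated choice to ignore one.

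A reader might also infer that the planned search for signatures of cure, non-response and safety events is compromised. The Microbiome Endpoints paragraph says that sequencing data feed that search and does not name the score. Any effect there would depend on a link that the documents do not make.

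A third tempting inference is a large loss of information. In an additive model with baseline variance equal to engraftment variance, reliability would be 1/(1+1) = 0.50, like losing half the sample. No figure in the documents supports that ratio, and SA4 expects depleted baselines. If they are uniformly depleted, the left-hand columns of the last table apply and the gain is negligible.

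Uniform depletion is, however, a hypothesis without data. Antibiotics and probiotics stop 3 days before FMT, bowel preparation can differ by route, and the consent description in section 6, VII-D allows the pre-FMT stool up to 3 days before. Baselines could therefore vary.

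Finally, the comparison with published healthy and dysbiotic samples does address general recovery, but outside the score and not against other study donors. It does not make the score donor-specific.

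**Conclusion.** The point holds as a free improvement to a secondary aim. Computed as written, the score credits both pre-existing resemblance and general recovery as engraftment of the donor used, and it does not say which donor applies after re-treatment. The gain from adjustment depends on baseline variation, which the documents do not give. In the illustration it runs from nothing (0.98 in both cases, shares up to 0.05) to 0.80 against 0.91 (shares up to 0.7). Those figures assume two communities with no shared taxa, uniform engraftment independent of baseline, and no measurement error. That the score contains no baseline term rests on none of these assumptions. Safety and cure endpoints are not touched.

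**What to change.** State the following in the Aim 4 analysis text:

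- **Score.** Analyse JSD between each post-FMT sample (Day 3, Week 6, Month 6, Month 12) and the donor unit received, with JSD between the Day 0 sample and that unit as a covariate. A proportional reduction from Day 0 is an acceptable alternative. Do not use the raw difference.
- **Donor specificity.** Report the same quantity beside it, computed against study donors the recipient did not receive.
- **Re-treated subjects.** Analyse samples taken after a second FMT separately, against the second donor. State that no stool is scheduled before a second FMT, so the last earlier sample may be a poor baseline.

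For first FMTs the cost is plan wording and analysis code. The baseline, follow-up and donor specimens are already planned for sequencing, and the unit or lot identifier is recorded on the Day 0 form. For re-treated subjects the fix adds no sample, so the weak baseline remains as a stated limitation.
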